PCRC PROPOSAL COVER SHEET

Title of Study or Project:	Association Between Driving Pressure and Postoperative Outcomes in Non-Cardiac Surgery Patients
Primary Institution:	Memorial Sloan Kettering Cancer Center, New York, NY
Principal Investigator:	[name]
Co-Investigators:	[name] [name] [name] [name]
Type of Study:	 Exploratory  Retrospective Observational  Prospective Randomized
IRB Number/Status:	Approved, IRB Exempt Protocol X18-028
Hypothesis:	Increased driving pressure during nonspontaneous mechanical ventilation will correlate with increased 30-day in-hospital mortality in a noncardiac surgery population
Number of Patients/Participants:	Estimated 85,000. (DataDirect query found 128,489 patients with 144,876 cases, and we estimate 1/3 loss of cases due to insufficient data.)
Power Analysis:	The primary hypothesis of interest is the effect of driving pressure in the presence of other covariates using multivariable logistic regression. We assume squared multiple correlation coefficient (R^2) of 0.3 to generate the variance inflation factor. Assuming an alpha of 0.05 and 10% event rate, an anticipated sample size of 85,000 will provide 95% power to detect an effect size of 0.049.
Proposed statistical test/analysis:	Multivariate logistic regression will be performed using the postoperative outcome of 30-day in-hospital mortality and driving pressure as the exposure to determine if an association exists. Secondary outcome analysis will focus on pulmonary complications defined by ICD 9/10 Codes. Variables including but not limited to age, gender, intubation time length, pulmonary disease, BMI, and ASA score will be analyzed.
Resources (Brief summary of resources for data collection, personnel, financial):	The MPOG database will be queried for the specified concept IDs with programmatic support from the MPOG Coordinating Center. Statistical analyses will be performed by biostatisticians from the MSKCC Department of Epidemiology & Biostatistics led by [name].

Introduction

What is the significance of the clinical problem being addressed?

Low tidal volume ventilation strategies based on ideal body weight gained prominence with the ARDSNet trial as a lung protective strategy and became widely adopted in critical care.¹ Over the last decade this strategy has also found acceptance in anesthesiology. However, it is important to remember that these results were from intensive care unit patients with acute respiratory distress syndrome (ARDS) who have far different lung mechanics than the surgical patient population. It is unclear that we can generalize the survival benefit of a tidal volume of 6 mL/kg of ideal body weight (IBW) versus 12 mL/kg IBW. There is data to suggest that by extrapolating this low tidal volume strategy to patients presenting to the operating room with healthy lungs, an increase in mortality in the setting of minimal positive end-expiratory pressure (PEEP) can be seen.² It is thought that this may be due to variations in lung compliance and that PEEP may be recruiting functional lung when properly titrated. Too much PEEP can cause barotrauma as well.³ Ideal body weight-based tidal volume ventilation strategies do not take respiratory compliance and the volume of aerated functional lung volumes into consideration.

Driving pressure (ΔP) is defined as the tidal volume (V_T) divided by respiratory-system compliance (C_{RS}), so $\Delta P = V_T / C_{RS}$. Driving pressure has been proposed as a possible solution to this problem since it is more reflective of compliance for each individual patient and has been shown to improve survival in a meta-analysis.⁴ A recent randomized controlled trial of driving pressure during thoracic surgery found that patients in the driving pressure group had fewer postoperative pulmonary complications.⁵

We hope to demonstrate that increased driving pressure will correlate with risk of increased mortality in the immediate perioperative time period for non-cardiac surgery patients. This may suggest that driving pressure may be a non-inferior/superior measure to monitor patients' intraoperative ventilatory status rather than low tidal volumes. Our primary outcome will be 30-day in-hospital mortality and its correlation to driving pressure with nonspontaneous mechanical ventilation. Cox and logistical regression analysis will be utilized to investigate this association. It will be important to take into consideration covariates that may confound conclusions and outcomes.

A secondary outcome will be the incidence of postoperative pulmonary complications (PPCs.) PPCs will be defined by a tiered categorization of ICD 9/10 codes for pulmonary complications as proposed by Douville *et al* (see appendix). PPCs include pneumonia, pulmonary edema, respiratory failure, and other complications. Length of stay will also be a secondary outcome.

30-day mortality was chosen as primary outcome instead of PPCs because it is more clearly defined and universally equivalent amongst institutions. Reporting of PPCs are more likely to be variable amongst institutions. The clinical significance of some PPCs on long-term outcome for patients is arguably less than 30-day mortality. Furthermore, the authors believe that if the null hypothesis were rejected for 30-day mortality that this would help advance the understanding of ventilatory strategies.

What current gaps exist in the understanding of this problem?

The theorized mechanism for low driving pressure being association with mortality is due to the belief that driving pressure corresponds to recruited lung size and therefore modulated by PEEP and tidal volume. Hyperinflation can lead to increased inflammatory markers and worse outcomes in ARDS.⁶ But under-recruited lung can be associated with increased mortality as well.² Similar to "euvoemia" in intravascular volume status management, optimized lung recruitment is difficult to define for each

individual patient but the definition and concept is clearer when talking in general terms. Current practice using tidal volumes of 6-8 mL/kg IBW may work for the population as a whole, but the nuance of individualized care for each patient may be lost. Does it make sense to ventilate the same tidal volume to a 60 kg otherwise healthy patient, a 60 kg end-stage emphysema patient, and a 60 kg patient with an obstructive bronchial tumor? Driving pressure presumably will be different for these different patients' lung compliances and better reflect functional lung volumes.

How will this project address this gap and advance clinical care and/or research knowledge?

The Multicenter Perioperative Outcomes Group (MPOG) database will allow us to conduct a multicenter retrospective look at the effect of driving pressure in surgical patients.

The specific goals of the project are as follows:

- 1) Investigate the association of driving pressure and 30-day in-hospital mortality in nonspontaneous mechanically ventilated non-cardiac surgical patients undergoing two lung ventilation.
- 2) Investigate the association of tidal volume in mL per kg IBW with 30 day in-hospital mortality and how this relationship is modified by driving pressure
- 3) Subgroup analysis: There are several patient subgroups that may play a role in modifying the association between driving pressure and mortality:
 - Pulmonary pressure using supraglottic airway devices (i.e. LMA's) may not be identical to endotracheal tubes given that the physiology is slightly different. We will analyze these two groups to determine if how the association to outcomes are modified.
 - Laparoscopic cases have increased extra-thoracic pressures on the lung due to insufflation which may not be analogous to increased pulmonary pressures due to ventilatory strategies.
 - Craniotomy cases sometimes are managed with hyperventilatory strategies to decrease intracranial pressures through hypocapnia. These hyperventilatory strategies may cause increased pulmonary pressure that is different from other types of cases and should be examined separately.
- 2) Secondary objective: Investigate the association of driving pressure and postoperative pulmonary complications within 30 days (presence of class 1, 2, or 3), and also length of stay.

Methods

Study Database and Population

MPOG is a non-profit academic consortium analyzing perioperative outcomes from hospitals in 18 states and 2 countries. Using electronic records including over 8.2 million anesthetic cases, MPOG facilitates analysis of the critical factors we are investigating regarding intraoperative respiratory variables and postoperative outcomes.

IRB statement

The project has been approved by the Memorial Sloan Kettering Cancer Center IRB under protocol X18-028.

Exposure Variables

- **Case Start:**
 1. Anesthesia Induction End (Concept 50005). If not available, then
 2. Anesthesia Induction Begin (Concept 50004). If not available, then
 3. Procedure Start (Concept 50006). If not available, then
 4. Patient in Room (Concept 50003). If not available, then
 5. Anesthesia Start (Concept 50002).
- **Case End:**
 1. Patient Extubated (Concept 50202). If not available, then
 2. Procedure End (Concept 50007). If not available, then
 3. Patient Out of Room (Concept 50008). If not available, then
 4. Anesthesia End (Concept 50009).

- Patients with a tracheostomy (in-situ or new) or in-situ endotracheal tube (Concept 50671). Supraglottic airways will be included in the study but examined more closely with secondary statistical analysis as described below.
- Patients with single-lung ventilation will be excluded
- Patients with presence of a double-lumen endotracheal tube or presence of bronchial blocker will be excluded
- Cardiac operations will be excluded
 - Anesthesia CPTs 00560, 00561, 00562, 00563, 00566, 00567, 00580
- All cases with cardiopulmonary bypass will be excluded
 - 50399 Cardiopulmonary bypass - aortic clamp on/off note
 - 50409 Cardiopulmonary bypass terminated
 - 50410 Cardiopulmonary bypass initiated (full)
 - 50416 Cardiopulmonary bypass - crossclamp and circulatory arrest time totals
 - 50417 Cardiopulmonary bypass - Access cannula removed note
 - 50714 Cardiopulmonary bypass - Bypass start / stop event
- Cases performed by cardiac surgical service (Concept 80005)
- Lung and liver transplant surgery will be excluded since they have unique pathophysiology to influence pulmonary complications:
 - Anesthesia CPT 00796 (liver), 00580 (lung)
- Highest base unit value of Anesthesia CPT is 3 or less.

Data source

An MPOG DataDirect query for cases meeting recording plateau pressure found 128,489 patients with 144,876 cases. We estimate 1/3 loss of cases due to insufficient data, so we expect approximately 85,000 patients with measured plateau pressure.

Statistical analysis

All patient demographic and clinical factors will be summarized using Number (%) and median (25th, 75th percentile) or mean (standard deviation) where appropriate. Summaries may be stratified by quantiles of driving pressure.

In the primary analyses, driving pressure will be recorded as the median of patient trajectory. The correlation between driving pressure and other ventilatory parameters (tidal volume, PEEP, plateau pressure etc.) will be quantified by the Spearman correlation coefficients.

The primary outcome is 30-day in-hospital mortality from the date of surgery, recorded as a binary outcome. Since MPOG data does not reliably have out of hospital mortality, we will assume mortality is only recorded in-hospital.

The primary exposure is driving pressure, recorded as the median of patient trajectory (continuous variable). The relationship between driving pressure and 30-day in-hospital mortality will be assessed with a multivariable logistic regression model, adjusting for preoperative and intraoperative factors. Confounders include but are not limited to age at surgery, gender, intubation time, ventilatory mode, airway device (i.e. endotracheal tube, LMA), pulmonary disease, BMI, ASA score. Potential non-linear relationship between driving pressure and the outcome will be examined using restricted cubic spline analysis. If a significant non-linear relationship between driving pressure and the outcome is detected, all subsequent analyses will include non-linear version of driving pressure. The non-linearity assumption will also apply to all other continuous variables across all analyses where appropriate.

If time to mortality is available, we will summarize the time to death (overall survival) as a survival endpoint using survival analysis approach: Kaplan-Meier curves to depict the pattern of survival over time and Cox proportional hazards model to assess the association between driving pressure and death adjusting for all relevant variables as done in the multivariable logistic model described above.

To address the second objective, the multivariable logistic regression model for 30-day mortality will include tidal volume in mL per kg of ideal body weight as well as its interaction with driving pressure, along with potential confounders. A significant interaction term will indicate that the relationship between tidal volume and 30-day mortality is moderated by driving pressure. The varying impact of the interaction between tidal volume and driving pressure on the probability of the primary outcome may be described graphically using quantiles of driving pressure.

Similarly, we will assess the interaction between driving pressure and 3 specific factors on the primary outcome: (1) supraglottic air way devices (i.e., LMAs) vs endotracheal tubes, (2) laparoscopic cases vs non-laparoscopic, and (3) craniotomy vs non-craniotomy cases. A significant interaction term will indicate that the relationship between driving pressure and the outcome is modified by these specific factors. Subsequent subgroup analyses will be performed in each subgroup to identify the impact of driving pressure specifically within each subgroup (i.e., driving pressure has a much larger impact on 30-day mortality among craniotomy cases than those observed among non-craniotomy cases). As a sensitivity analysis, we will also perform the primary analysis after exclusion of emergency surgery cases.

Secondary outcomes include postoperative pulmonary complications (PPCs) within 30 days (presence of class 1, 2, or 3) and length of stay. PPCs will be analyzed using multivariable logistic regression, while length of stay will utilize Poisson regression. All models will include driving pressure as the variable of interest, adjusting for the same factors as in the primary analyses. As above, we will assess the interaction between driving pressure and tidal volume to investigate the presence of modification of the relationship between tidal volume and the outcome by the driving pressure.

The primary exposure variable (driving pressure) is defined as the median of patient driving pressure values collected intraoperatively. In an exploratory manner, we plan to investigate other methods to quantify driving pressure that is informative of the outcome and can provide clinical relevance. One alternative is to utilize the cumulative number of minutes with a driving pressure over 15 cmH₂O, based

on findings in acute respiratory distress syndrome patients.⁴ Another alternative is to consider the area under the curve (of the continuously measured driving pressure) for each patient.

Power analysis

We estimate that 85,000 cases may be available for analysis. For the binary outcome of 30-day mortality, we present a power analysis based on a multivariable logistic regression following the procedure by Hsieh et al.⁷ The primary hypothesis of interest is the effect of driving pressure in the presence of other covariates (see statistical analysis for a list of potential confounders). In the following power analysis, we assume squared multiple correlation coefficient (R^2) of 0.3 to generate the variance inflation factor. Assuming an alpha of 0.05 and 10% event rate, this sample size will have 95% power to detect an effect size of 0.049.

We present a few scenarios for reference: If the number of cases available was reduced to 40,000 cases, we will have 95% power to detect an effect size of 0.072. With the same sample size but higher R^2 , we will have 95% power to detect an effect size of 0.085. If instead, the event rate was lowered to 5% and R^2 is reduced to 0.1, the anticipated sample size of 85,000 cases will provide 95% power to detect an effect size of 0.060.

Variables to be collected

Variable	Description	Data Type	Location
Age	Age in years	Integer	View [Case_Demographics]
Gender	Gender	String	View [Case_Demographics]
ASA Physical Status	ASA Physical Status	Integer	Concept 70233
Emergent	Emergent status	Boolean	Concept 70233
Weight	Weight (kg)	Number	View [Case_Anthropometrics]
Height	Height (cm)	Number	View [Case_Anthropometrics]
Smoking Status			
Surgical Admission Type	Surgical Admission Type	String	Column AIMS_Admission_Type
Year of service	Year of surgical date of service	Integer	Column AIMS_Scheduled_DT
Length of Stay	Length of stay in days	Number	Billing data
Chronic pulmonary disease?	Presence of chronic pulmonary disease (Elixhauser) in diagnosis codes	Boolean	Billing data
Inhaled steroid?	Presence of inhaled steroid in home medication list	Boolean	Home medication list
Laparoscopic procedure?	Is procedure laparoscopic, based on CPT code	Boolean	
Procedural service		String	Column AIMS_Primary_Procedural_Service
Procedure name		String	
Craniotomy procedure?	Is procedure a craniotomy, based on CPT code	Boolean	
Prone Position?	Whether position is prone		Unclear source – 50136 Positioning? or 50692 – categorized note positioning
Surgery Duration	First procedure start to last procedure finish, in minutes	Integer	View Case_Times
ETT Type	Endotracheal tube type	String	Concept 50123 ETT Type
LMA Type	LMA type	String	Concept 50141 LMA Type
Ventilation Mode	Ventilation mode	String	Concept 3182 Ventilator Mode (most common for case)
Intubation Time	First Intubation time (as minutes)	Integer	Concept 50695 Categorized note Intubation

	from anesthesia start)		
Extubation Time	Last Extubation Time	Integer	Concept 50202 – Emergence Patient Extubated
Reversal Time	Time of administration of NMB reversal	Integer	Concept 10739 – Sugammadex Concept 10315 – Neostigmine Concept 10383 – Pyridostigmine
Median tidal volume	Median TV	Integer	Concept 3190 – Tidal Volume Actual
Median respiratory rate	Median respiratory rate	Integer	Concept 3580 – RR
Median peak inspiratory pressure	Median peak inspiratory pressure	Integer	Concept 3185 – PIP
Median plateau inspiratory pressure	Median plateau inspiratory pressure	Integer	Concept 3186 – Plateau IP
Median PEEP	Median Positive End Expiratory Pressure	Integer	Concept 3210 – PEEP Measured
Median EtCO ₂	Median end tidal carbon dioxide	Integer	Concept 3235 – EtCO ₂ (mmHg)
Median FiO ₂	Median Fraction of Inspired Oxygen	Integer	Concept 3200 – Ventilator FiO ₂ Measured
Mortality (days)	Days from Date of Surgery to Date of Death	Integer	Mortality Table
Pulmonary Complications	See Appendix for ICD Diagnosis codes associated with Pulmonary Complications		

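### The form of driving pressure in the primary model is chosen by a significance test on the same outcome data, so if the chosen form supplies the primary test, its type I error exceeds 0.05 (about 6-8% under conventional settings).

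*Protocol*

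**What the plan says.** The primary model is set out in the protocol's Statistical analysis section: "The relationship between driving pressure and 30-day in-hospital mortality will be assessed with a multivariable logistic regression model". Driving pressure is the case median, treated as continuous. The same paragraph goes on: "Potential non-linear relationship between driving pressure and the outcome will be examined using restricted cubic spline analysis". It then states the rule that matters here. "If a significant non-linear relationship between driving pressure and the outcome is detected", every analysis that follows is to use the non-linear form.

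The Power analysis section describes one target: "The primary hypothesis of interest is the effect of driving pressure in the presence of other covariates". Its settings are "Assuming an alpha of 0.05 and 10% event rate", and "we assume squared multiple correlation coefficient (R^2) of 0.3 to generate the variance inflation factor". The result is that "this sample size will have 95% power to detect an effect size of 0.049", where the sample size is 85,000 cases.

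The protocol gives no level for the non-linearity test, no number or position of knots, and no statement of which test carries the primary hypothesis once the spline has been chosen. Such details are commonly left to a statistical analysis plan and their absence is not the point. The point is the rule that the protocol does state: test first, then choose the form.

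**The concern.** Under this rule the primary hypothesis can be rejected by two routes. If the non-linearity test is not significant, the linear coefficient is tested. If it is significant, the spline terms are tested. The data sets sent down the second route were picked because their non-linear component was large, and that component is part of the joint spline statistic. The joint test is then referred to a critical value that takes no account of this.

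The power calculation treats driving pressure as a single coefficient at alpha 0.05. The Introduction also ties the study's value to rejecting the null hypothesis for 30-day mortality. At stake is whether the nominal 5% is the error rate of the test that will be reported.

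**Working it through.** **1. The plan's own figure.** The method cited in the protocol for logistic regression gives, two-sided, b = (z₀.₉₇₅ + z₀.₉₅) / √[N·P(1−P)·(1−R²)], with b the log odds ratio per standard deviation of driving pressure. Inputs from the Power analysis section: N = 85,000, P = 0.10, R² = 0.3, power 95%.

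- Denominator: 85,000 × 0.09 × 0.7 = 5,355, whose square root is 73.18.
- b = 3.605 / 73.18 = 0.0493, against 0.049 stated.

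A one-sided test would give 0.045, so the stated figure is a two-sided test of one linear term at 0.05.

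**2. Type I error of the test-then-choose rule.** With k knots the spline has k−1 terms: one linear and k−2 non-linear. Under no association, the linear statistic Z² (1 df) and the non-linearity statistic Q (k−2 df) are asymptotically independent. Let a be the level of the non-linearity test, c its critical value on k−2 df, and J the 5% critical value of the joint test on k−1 df. Then

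type I error = (1−a) × 0.05 + P(Q > c and Z² + Q > J).

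Assumed, because the protocol does not state them: a = 0.05, k = 3 to 5, and a joint test of all spline terms once the spline is chosen. The linear branch contributes 0.95 × 0.05 = 4.75% in every case.

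| Knots | Linear branch | Spline branch | Total | Joint test's rejection rate among data sets sent to the spline |
|---|---|---|---|---|
| 3 | 4.75% | 2.49% | 7.2% | 50% |
| 4 | 4.75% | 3.05% | 7.8% | 61% |
| 5 | 4.75% | 3.34% | 8.1% | 67% |

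The last column is the spline-branch contribution divided by 5%. It shows the mechanism: after selection, a test meant to reject 5% of null data sets rejects half to two thirds of them.

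**3. Checks.** Four million chi-square draws gave 7.24%, 7.80% and 8.10% for 3, 4 and 5 knots. A simulation of 4,000 covariate-adjusted logistic data sets (10,000 cases each, roughly 10% events) gave 7.5%, 8.5% and 8.6%, with a Monte Carlo standard error of about 0.4 points.

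**4. Sensitivity to the assumed level, 3 to 7 knots.**

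| Level of non-linearity test | Type I error |
|---|---|
| 0.001 | 5.1% |
| 0.01 | 6.0% |
| 0.05 | 7.2-8.4% |
| 0.10 | 7.5-8.8% |
| 0.20 | 7.5-8.6% |

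The 0.01 row can be checked by hand. A Q beyond its 1% critical value already exceeds J (for 3 knots, 6.63 against 5.99), so every data set sent to the spline is rejected: 0.99 × 0.05 + 0.01 = 5.95%.

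**5. With the form fixed in advance.** Always linear, or always the spline with one joint test, gives 5.0% in theory. The logistic simulation gave 5.2% for the linear term and 5.3-5.5% for the joint test.

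**6. Price of the joint test.** The non-centrality needed for 95% power at alpha 0.05 is 12.99 on 1 df, 15.44 on 2 df and 17.17 on 3 df. Dividing by 5,355 and taking the square root gives detectable linear effects of 0.049, 0.054 (3 knots) and 0.057 (4 knots).

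**The case against.** **The primary test may be meant to stay linear.** The switch applies to subsequent analyses, which could mean only what follows in the section: the Cox model, the interactions and the secondary outcomes. On that reading the primary test keeps its 5%. The wording allows this, but the rule stands in the primary-model paragraph and nothing says that the linear term remains primary. What stands is that the inflation is conditional on the other reading.

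**The size depends on unstated settings.** This is correct. A strict non-linearity test at 0.001 would make the excess negligible. At conventional levels the direction does not change.

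**Checking for curvature is good practice, and the rule was announced beforehand.** Both are true. The Introduction describes harm from hyperinflation and from under-recruitment, so a non-monotone curve is plausible. The criticism is not of the check but of letting it choose the primary test. Announcing the rule in advance does not restore the error rate.

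**The study is retrospective and observational.** That limits the practical weight of 2 to 3 percentage points. The protocol nevertheless names one primary hypothesis and an alpha for it.

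Two stronger readings are tempting and are not supported:

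- A reader might infer that a significant non-linearity test would itself count as a positive finding, for an error of 1 − 0.95² = 9.75%. The protocol nowhere says so.
- A reader might infer that all confidence intervals after selection are too narrow. Under the null the linear and non-linear statistics are independent, so the linear branch keeps its 5% error and its interval is not affected. The criticism applies to the spline branch only.

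**Conclusion.** The point holds in conditional form. The protocol lets a test on the outcome data choose between a linear and a spline term and fixes no single primary test. If the selected form supplies the primary test, the type I error is about 7-8% in place of 5%, assuming a 5% non-linearity test, 3 to 5 knots and a joint spline test. It is about 6% with a 1% non-linearity test. The excess lies wholly in data sets routed to the spline, where p-values and intervals ignore the selection. An unconditional statement that the primary test runs at 7-8% would go further than the document allows, since the settings are unstated and the text can be read as leaving the primary test linear. This is a moderate defect in a stated rule, worth correcting because the correction is cheap. The same rule is extended to the other continuous variables; that is not part of this calculation.

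**What to change.** Replace the test-then-choose sentence with one fixed form and one fixed test. Enter driving pressure as a restricted cubic spline with the number and percentiles of the knots stated in advance (3 or 4). Base the primary p-value on a single joint test of all driving-pressure terms at 0.05. Report the fitted curve and odds ratios at fixed contrasts whatever the non-linearity test shows, and use that test only to describe the shape.

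This changes analysis wording only; data and sample size are untouched. It restores the 5% error rate. The cost is the rise in the detectable linear effect at 95% power from 0.049 to 0.054 or 0.057, and the Power analysis section should be updated to match.

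The alternative is to state that the linear term is the primary test whatever the non-linearity test shows, with the spline as supportive. That agrees with the power calculation as written and costs nothing if the relation is close to linear, but it loses power if the true relation is not monotone.

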Appendix: Inhaled Steroids and Tradenames

Beclomethasone	QVAR, Beconase Aq, Becotide, Beclocort
Flunisolide	Aerospan
Fluticasone	Flovent, Advair Diskus, Arnuity Ellipta
Budesonide	Pulmicort
Fluticasone-salmeterol	Advair HFA
Budesonide-formoterol	Symbicort
Mometasone	Asmanex
Ciclesonide	Alvesco, Zetonna
Formoterol-mometasone	Dulera
Fluticasone-vilanterol	Breo Ellipta, Relvar Ellipta
fluticasone/umeclidinium/vilanterol	Trelegy Ellipta

Handling of missing data and artifacts

Patterns of missingness will be summarized. We expect low proportion of missing data in the primary endpoint as it is one that is clearly defined and conventionally reported. Similarly, we expect low missingness in intraoperative measures. We will investigate whether the missingness is missing completely at random or missing at random. In the absence of informative missingness, we will proceed with complete-case analyses. Otherwise, multiple imputation will be performed.

Medians will be used to summarize tidal volume and pressure data. Zero value artifacts will be removed. For tidal volumes we will remove values less than 2 mL/kg and more than 20 mL/kg. Only values between intubation and extubation will be used in these medians.

Areas for discussion/known limitations

- Alternative methods for selecting a patient's index case are:
 - First surgery for patient (current proposal)
 - Remove all patients with repeat surgeries
 - Surgery with longest ventilator duration (maximum exposure)
 - First surgery during admission or 30-day period (possibly multiple cases per patient, if multiple admissions)
 - Surgery with highest anesthesia CPT base unit value
- There will be selection bias since not all locations report all the included data.
- We will exclude one-lung ventilation patient group since they may represent a significantly different patient population and pulmonary physiology. Why not focus on sicker patients?
 - Our study focuses on the noncardiac surgery patient population in general and assumes ventilatory management can have impact on patients 30-day mortality. While the broadness of our study is a strength, it also introduces a possibility that a signal may be drowned in the noise of its large, heterogenous patient population. Focusing on only high-risk groups opens the criticism that finding a correlation will only show that “sick patients are more likely to be sicker.”

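### Apart from ASA class, chronic lung disease is the only comorbidity requested, so other chronic illness is adjusted for only indirectly, in a study aimed at a very small effect

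*Protocol*

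**What the plan says.** The table under Variables to be collected in the Protocol has one comorbidity drawn from diagnosis codes: "Presence of chronic pulmonary disease (Elixhauser) in diagnosis codes", sourced from billing data. It also lists "ASA Physical Status", emergent status, height and weight, smoking status, admission type, home inhaled steroids, procedural service and procedure name. It has no field for heart, kidney, liver or malignant disease.

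Under Statistical analysis, the primary logistic model adjusts for an open list of confounders. The patient-health items named are age, gender and "pulmonary disease, BMI, ASA score". The PPC and length-of-stay models reuse the same factors. Patients with ASA 5 or greater are excluded. The cover sheet says the registry will be queried for the concept IDs that the protocol specifies.

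Under Areas for discussion/known limitations, the authors explain why they do not restrict to high-risk groups: a correlation found there could be dismissed as showing only that "sick patients are more likely to be sicker".

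The Power analysis section states: "Assuming an alpha of 0.05 and 10% event rate, this sample size will have 95% power to detect an effect size of 0.049".

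**The concern.** The introduction defines driving pressure as tidal volume divided by respiratory-system compliance. A chronic illness that lowers compliance therefore raises the exposure. If it also raises in-hospital mortality, it confounds the primary association. The plan measures chronic illness separately only where it is pulmonary. Everything else must be carried by ASA class, which has at most four levels after the exclusion.

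The planned effect is small: exp(0.049) is an odds ratio of about 1.05 per SD. At 85,000 cases the standard error is small too, so a modest leftover imbalance could produce a significant coefficient that reads as an effect of ventilation. The criticism the authors foresee for high-risk groups would then apply to their own cohort. The secondary models share the adjustment set and so share the exposure to this bias.

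**Working it through.** **1. Reproducing the plan's figure.** The Protocol's Power analysis section gives the inputs: "We estimate that 85,000 cases may be available for analysis", 10% events, alpha 0.05, power 95%, and "we assume squared multiple correlation coefficient (R^2) of 0.3 to generate the variance inflation factor". The method is the Hsieh formula for a continuous covariate, so the effect is a log odds ratio per SD.

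- SE = 1/√(N·P·(1−P)·(1−R²)) = 1/√(85,000 × 0.10 × 0.90 × 0.70) = 1/√5,355 = 0.01367
- Detectable effect = (1.960 + 1.645) × 0.01367 = 0.0493, against 0.049 stated

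Sidedness is not stated. Two-sided alpha reproduces the figure; one-sided would give 0.0450.

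For the protocol's scenario with 5% events and R² 0.1, SE = 1/√(85,000 × 0.05 × 0.95 × 0.90) = 0.0166. The detectable effect is 0.0598, against 0.060 stated.

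**2. Bias from one omitted condition.** The documents give no figures for any comorbidity, so the inputs here are assumptions shown as a range:

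- p: prevalence of the condition
- d: its shift in driving pressure, in SD, remaining after ASA and the other covariates
- OR: its odds ratio for death, remaining after the same covariates

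Bias per SD ≈ ln(OR) × p(1−p) × d/(1−R²)

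Example at the base values: 0.693 × 0.10 × 0.90 × 0.3/0.70 = 0.0267.

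**3. False rejection when the true effect is zero.** This is P(|Z + bias/SE| > 1.96). In the example, bias/SE = 1.956, which gives 50%.

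| p | d (SD) | OR | Bias, base | Share of 0.049 | False rejection, base | Bias, 5% events and R² 0.1 | False rejection, 5% events and R² 0.1 |
|---|---|---|---|---|---|---|---|
| 5% | 0.2 | 1.5 | 0.0055 | 11% | 7% | 0.0043 | 6% |
| 10% | 0.2 | 1.5 | 0.0104 | 21% | 12% | 0.0081 | 8% |
| 10% | 0.2 | 2.0 | 0.0178 | 36% | 26% | 0.0139 | 13% |
| 10% | 0.3 | 2.0 | 0.0267 | 55% | 50% | 0.0208 | 24% |
| 15% | 0.3 | 2.0 | 0.0379 | 77% | 79% | 0.0295 | 43% |

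The nominal rate is 5%. With 40,000 cases and R² 0.3 the biases are as in the base column, and false rejection is 6%, 8%, 15%, 27% and 48%.

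**4. Checks on the approximation.** Logistic simulations of the five base rows (2,000,000 records) gave 0.005, 0.009, 0.022, 0.033 and 0.043, with Monte Carlo SE about 0.003. The linear formula is adequate for order of magnitude.

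A second simulation (1,000,000 records, SE about 0.004, no covariates other than the grade) put a four-level ASA-like grade in the model. There p = 20%, OR = 2 and d = 0.3 are the values before any adjustment for the grade. The bias was 0.041 with an uninformative grade, 0.032 with a moderately informative one and 0.022 with a strongly informative one. ASA can therefore remove a material part without removing all of it. At the base SE, biases of 0.032 and 0.022 still give about 65% and 36% false rejection.

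**The case against.** A reader might infer that non-pulmonary disease cannot be adjusted for at all. The documents do not support that. ASA status is a global grade of systemic illness, it is collected, and it is named in the primary model. BMI is in the model, smoking and emergent status are collected, and a sensitivity analysis drops emergency cases.

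A reader might also infer that the bias will be close to the target effect. Only the most extreme row approaches it, and every input is assumed. The protocol supports a link between compliance and driving pressure. It does not say that kidney, liver or malignant disease changes compliance once BMI, ASA and lung disease are in the model. Nor can biases from several conditions simply be summed, since they may differ in sign and overlap through ASA. The formula also uses the full variance p(1−p); to the extent that ASA, age and BMI predict the condition, the bias is smaller. All of this stands and limits the point.

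The remaining objection is that the table is a working list. Confounders are left open, Set PEEP is used under Exposure Variables but missing from the table, and one row is marked as having an unclear source. This does not remove the point. Set PEEP is specified elsewhere with its concept ID, whereas no other comorbidity is specified anywhere. An analysis plan can choose among extracted variables but cannot use conditions that were never requested.

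**Conclusion.** The point holds in a limited form. Run as written, the plan leaves non-pulmonary chronic illness to ASA class, in an observational model aimed at a log odds ratio of 0.049 per SD. Residual confounding from conditions that lower compliance and raise mortality is possible, not demonstrated.

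Under the assumed inputs, one such condition gives a bias of about 0.006 to 0.038 at the base planning values. False rejection under a null effect is about 7-79% there and 6-43% with 5% events and R² 0.1. These figures rest on assumed associations left over after ASA and on the linear approximation. If deaths are fewer than planned, false rejection falls, but the bias in the odds ratio does not go away. This is a cheap improvement to make before extraction; it does not show that the primary analysis is invalid.

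**What to change.** In Variables to be collected, extend the chronic-pulmonary-disease row to the other chronic Elixhauser comorbidity flags, from the same billing diagnosis codes, keeping chronic pulmonary disease as its own flag. Name these flags in the adjustment set of the primary model, and hence of the PPC and length-of-stay models. If deaths are few, use one score built from them. At the planning values 85,000 × 0.10 = 8,500 deaths are expected, so separate flags should be affordable. Report the driving-pressure odds ratio with and without the flags, which shows directly how much ASA left unadjusted.

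The cost is an extended data request and more covariates, using a source and method already planned, with no new patients. The downside is that index-stay codes may include conditions that arose after surgery, and adjusting for those could remove part of a real effect. Restrict to chronic-condition flags and use present-on-admission or earlier-encounter codes if available; the protocol does not say whether they are. If they are not, present the comorbidity-adjusted model as a sensitivity analysis.
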